8.3.4 Regulatory reporting requirements for SAEs

Prompt notification (24 hours) by the Investigator to the Sponsor of a SAE is essential so that legal obligations and ethical responsibilities towards the safety of participants and the safety of a study treatment under clinical investigation are met.

The Sponsor has a legal responsibility to notify both the local regulatory authority and other regulatory agencies about the safety of a study treatment under clinical investigation. The Sponsor will comply with country-specific regulatory requirements relating to safety reporting to the regulatory authority, Institutional Review Boards (IRB)/Independent Ethics Committees (IEC), and investigators.

Investigator safety reports must be prepared for suspected unexpected serious adverse reactions (SUSAR) according to local regulatory requirements and Sponsor policy and forwarded to investigators as necessary.

An Investigator who receives an investigator safety report describing a SAE or other specific safety information (eg, summary or listing of SAEs) from the Sponsor will review and then file it along with the IB and will notify the IRB/IEC, if appropriate according to local requirements.

8.3.5 Pregnancy

Details of all pregnancies in female participants and, if indicated, female partners of male participants will be collected after the start of study treatment and until 90 days after the last dose.

If a pregnancy is reported, the Investigator must immediately inform the Sponsor within 24 hours of learning of the pregnancy and should follow the procedures outlined in Appendix 4 (Section 10.4).

The participant should be withdrawn from the study as soon as pregnancy is known (by positive pregnancy test), and the following should be completed:

- The participant should return for an early discontinuation (PEOT) visit.

Abnormal pregnancy outcomes (eg, spontaneous abortion, fetal death, stillbirth, congenital anomalies, ectopic pregnancy) are considered SAEs.

8.3.6 Adverse events of special interest

An AESI is any AE that a regulatory authority has mandated be reported on an expedited basis, regardless of the seriousness, expectedness, or relatedness of the AE to the administration of a UCB product/compound. For rozanolixizumab, the following events require immediate reporting (within 24 hours regardless of seriousness) to UCB:

- Hy's Law
 - Potential Hy's Law, defined as $>3\times\text{ULN}$ ALT or AST with coexisting $>2\times\text{ULN}$ total bilirubin in the absence of $<2\times\text{ULN}$ ALP, with no alternative explanation for the biochemical abnormality (ie, without waiting for any additional etiologic investigations to have been concluded). Follow-up information should be reported if an alternative etiology is identified during investigation and monitoring of the participant.

All AESIs will follow the SAE recording and reporting procedures as indicated in Appendix 3 (Section 10.3).

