3.9 Changes to protocol-defined analyses

In the protocol section 9.2.1, the intercurrent events to be considered are the use of rescue therapy prior to Day 43 and permanent treatment discontinuation (or withdrawal from study) due to TEAEs. In the SAP, we consider use of rescue therapy prior to Day 43 and permanent treatment discontinuation due to TEAEs as intercurrent events.

In the protocol, the treatment policy strategy is described for the analysis meaning that all data was planned to be analyzed regardless of study participants receiving treatment with rescue therapy. Summaries will also be presented for the efficacy endpoints where participants will be censored at the time that they take rescue medication. In the SAP, time to MG-ADL response will be analyzed censoring the data at the time of the use of rescue therapy and all other efficacy endpoints will be summarized following treatment policy.

Protocol amendment 3 did not mention how to treat IgG when participants receive rescue therapy. In the SAP, the IgG values up to and including 8 weeks after start date of rescue therapy will be excluded from the analysis.

In the protocol section 8.3.1, Hy's law is defined as $>3 \times \text{ULN}$ ALT or AST with coexisting $>2 \times \text{ULN}$ total bilirubin in the absence of $<2 \times \text{ULN}$ ALP, with no alternative explanation for the biochemical abnormality (ie, without waiting for any additional etiologic investigations to have been concluded). In this SAP, Hy's law is defined as (AST or ALT $\geq 3 \times \text{ULN}$) and TBL $\geq 2 \times \text{ULN}$ and ALP $< 2 \times \text{ULN}$ to be consistent with Rozanolixizumab program SAP.

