- Incidence of Non-TEAEs leading to discontinuations

AESMs include severe and/or serious headache and suspected aseptic meningitis.

AESIs are the cases of potential Hy's Law (see [Section 8.3.1](#)).

AESMs and AESIs will be identified based on the assessment by the Investigator as recorded in the CRF. An AE will be counted as an AESM if there is a 'yes' response to the question "Adverse event of Special Monitoring?" and 'no' otherwise. An AE will be counted as an AESI if there is a 'yes' response to the question "Adverse Event of Special Interest?" and 'no' otherwise.

When applicable adverse event summaries will be ordered by alphabetical SOC, alphabetical HLT within SOC and decreasing frequency of PT in the RLZ total column for tables.

Listings of all TEAEs, all non-serious TEAEs, serious TEAEs, permanent withdrawal of IMP due to TEAEs, study participant discontinuation from study due to TEAEs, AEs leading to death, AESIs, AESMs, intermittent period AEs, persistent AEs, non TEAEs and TEAEs for participants who used manual push will be presented by treatment group, study cycle and participant. Most recent dose will be presented in listing even when the AE start date is partial. A flag will be added in those listings to highlight whether the AE occurred on manual push or not.

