8.3.1 Potential drug-induced liver injury

The number and percentage of study participants who meet one or more of the following potential drug-induced liver injury (pDILI) criteria during TE period will be summarized by entire study, actual treatment group at the time of meeting the following criteria and RLZ total:

- Participants with at least one post-Baseline liver laboratory assessment
- Incidence of potential hepatotoxicity with symptoms potentially associated with hepatitis or hypersensitivity
- Incidence of potential hepatotoxicity with no symptoms potentially associated with hepatitis or hypersensitivity
- Laboratory criteria for pDILI:
 - (AST or ALT $\geq 3 \times$ ULN) and TBL $\geq 1.5 \times$ ULN
 - (AST or ALT $\geq 3 \times$ ULN) and TBL $\geq 2 \times$ ULN
 - (AST or ALT $\geq 3 \times$ ULN) and TBL $\geq 2 \times$ ULN and ALP $< 2 \times$ ULN (Hy's Law)

In order to meet the above criteria, a study participant must experience the elevation in bilirubin and ALT or AST (and the absence of the ALP elevation) at the same visit. For example, a study participant who experiences a $\geq 2 \times$ ULN elevation of bilirubin at one visit and a $\geq 3 \times$ ULN elevation in ALT (or AST) at a subsequent visit has not fulfilled the Hy's law criteria. If participant meets part of one criterion but at least one parameter is unknown, then he/she should not be considered for meeting the criterion.

Additional analyses for liver function tests (LFTs) will be performed to assess the potential for liver toxicities in accordance with the United States Food and Drug Administration guidelines. Per guidelines, the following criteria will be used to define levels of LFT elevation:

- Aspartate aminotransferase (AST): $>3 \times$ ULN, $>5 \times$ ULN, $>8 \times$ ULN, $>10 \times$ ULN, $>20 \times$ ULN
- Alanine aminotransferase (ALT): $>3 \times$ ULN, $>5 \times$ ULN, $>8 \times$ ULN, $>10 \times$ ULN, $>20 \times$ ULN
- AST or ALT: $>3 \times$ ULN, $>5 \times$ ULN, $>8 \times$ ULN, $>10 \times$ ULN, $>20 \times$ ULN
- Total bilirubin (TBL): $>1.5 \times$ ULN, $>2 \times$ ULN
- Alkaline phosphatase (ALP) $>1.5 \times$ ULN

The number and percentage of study participants who meet one or more of the above LFT elevation criteria during TE period will be summarized by entire study, actual treatment group at the time of meeting the above criteria and RLZ total.

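### The ALP condition for potential Hy's Law in Protocol 8.3.6, read literally, is the reverse of the one in SAP 8.3.1, so the AESI and laboratory Hy's Law counts cannot be assumed to reconcile

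*Protocol*

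**What the plan says.** - **Protocol 8.3.6 (the rule sites work from).** Potential Hy's Law is ALT or AST >3xULN with total bilirubin >2xULN, "in the absence of $<2\times\text{ULN}$ ALP", and "with no alternative explanation for the biochemical abnormality". It must be reported to the sponsor within 24 hours whatever its seriousness. It is the only AESI listed.
- **SAP 8.3.1 (laboratory table).** The Hy's Law row is AST or ALT >=3xULN and bilirubin >=2xULN "and ALP $< 2 \times$ ULN (Hy's Law"). The explanatory text asks for the transaminase and bilirubin elevations "and the absence of the ALP elevation) at the same visit".
- **SAP 8.2.2 (AESI table).** It first ties the two together: "AESIs are the cases of potential Hy's Law", with a pointer to SAP 8.3.1. It then sets the data source: "AESMs and AESIs will be identified based on the assessment by the Investigator as recorded in the CRF". The resulting treatment-emergent AESI table is planned for the entire study, and SAP 11.6 repeats it for Japan.
- **SAP 3.9 (changes from protocol).** It restates both definitions and adopts its own "to be consistent with Rozanolixizumab program SAP". It places the protocol text in section 8.3.1, although it stands in 8.3.6, and does not remark that the ALP conditions point in opposite directions.
- **Protocol Appendices 2 and 6.** A separate rule for possible Hy's Law requires SAE reporting for ALT >=3xULN with bilirubin >=2xULN (more than 35% direct), or ALT >=3xULN with INR >1.5. It has no ALP condition.

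**The concern.** The protocol phrase is a double negative. The absence of an ALP below 2xULN means an ALP of at least 2xULN, whereas the SAP asks for an ALP below 2xULN. SAP 3.9 reproduces the protocol phrase, so this is not a fault of text extraction.

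The discrepancy can reach an output because the AESI table is filled from the investigator's answer and not from laboratory values. The SAP therefore gives AESIs one meaning, while the site document that governs the answer literally gives the opposite. No planned step compares the two. At stake are the treatment-emergent AESI table and AESI expedited reporting. Potential Hy's Law is the only AESI, so every entry in that table depends on this definition.

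**Working it through.** The documents give no figure on this point, so the check is logical, with a small enumeration.

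**Rules at one visit, in multiples of ULN (T = transaminase, B = total bilirubin):**

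- P (Protocol 8.3.6, literal): T >3, B >2, not (ALP <2)
- S (SAP 8.3.1): T >=3, B >=2, ALP <2
- A (Appendices 2 and 6, simplified): T >=3, B >=2, no ALP term; the direct-bilirubin and INR conditions are left out

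**Step 1, single visit.** P needs ALP >=2 and S needs ALP <2. No ALP value satisfies both, so P and S exclude each other at any one visit, whatever the other values.

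**Step 2, enumeration.** Assumed values around the cut-offs are T = 2.9, 3.0, 3.1, 5, 10; B = 1.9, 2.0, 2.1, 4; ALP = 0.8, 1.5, 1.9, 2.0, 2.1, 4. That gives 5 x 4 x 6 = 120 points.

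- P: 3 x 2 x 3 = 18 points
- S: 4 x 3 x 3 = 36 points
- P and S together: 0 points
- A: 4 x 3 x 6 = 72 points, including all of P and all of S

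**Step 3, what remains once ALP is aligned.** Give both rules the same ALP condition. The protocol rule then meets 18 points, all inside the SAP rule's 36. The other 18 all have T exactly 3 or B exactly 2, which is the > versus >= difference. The grid has three ALP values on each side of 2, so these counts do not depend on which ALP condition is used.

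**Step 4, illustrative cases.** P also assumes that no alternative explanation exists.

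| Case | Protocol AESI, literal | SAP Hy's Law row | SAP row without ALP (T >=3, B >=2) | Appendix SAE rule |
|---|---|---|---|---|
| ALT 4, B 2.5, ALP 1 | no | yes | yes | yes, if direct bilirubin >35% |
| ALT 4, B 2.5, ALP 3 | yes | no | yes | yes, if direct bilirubin >35% |
| AST 4, ALT 2, B 2.5, ALP 1, INR normal or unmeasured | no | yes | yes | no |

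The third case limits what Step 2 says about A. The grid uses one transaminase value, but the appendix rule names ALT only, so it does not cover cases driven by AST.

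**Step 5, participant level.** Take ALT 6 and B 3 at two visits, with ALP 1.5 and then 2.5. This participant meets S at the first visit and P at the second. Mutual exclusion therefore holds per visit and not per participant.

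**The case against.** A reader might infer that the AESI table and the laboratory Hy's Law table must describe disjoint sets of cases. The documents do not support that, for three reasons.

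- Both tables count participants, who can qualify under each rule at different visits (Step 5).
- The laboratory table in SAP 8.3.1 also has a row with no ALP condition. Within the treatment-emergent period, every literal protocol case falls in that row, and a listing shows the results at the visit.
- The AESI table follows the investigator's judgement. Whether investigators apply the double negative literally is an assumption. The CRF completion guidelines are not among the documents, and SAP 8.2.2 itself points to SAP 8.3.1.

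The other side can add that SAP 3.9 sets the two definitions side by side, so the difference is disclosed. Many cases driven by ALT would reach the sponsor anyway, through the appendix SAE rule and the 24-hour reporting attached to the liver stopping criteria. AESI occurrence is not a listed endpoint, all analyses are descriptive, and the laboratory Hy's Law count does not depend on any CRF answer.

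Most of this stands, and it limits the consequence. It does not remove the defect. SAP 3.9 neither names the reversal nor changes what sites are told. The SAE route misses cases driven by AST, depends on the direct-bilirubin fraction or INR, and does not set the AESI flag. If some investigators follow the text and others correct it in their heads, the AESI table mixes opposite definitions.

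**Conclusion.** The concern holds as an inconsistency between two operative definitions. At a single visit they are mutually exclusive as written (0 shared points out of 120, and none possible for any values). Apart from ALP and the protocol's clinical qualifier, they differ only at exactly 3xULN transaminase or 2xULN bilirubin.

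The consequence is conditional. If sites apply the protocol wording, the treatment-emergent AESI table and AESI expedited reporting may omit cases that the SAP calls Hy's Law or include cases with ALP >=2xULN. The AESI and laboratory counts cannot then be assumed to reconcile. The documents support neither disjoint tables nor a general failure of expedited reporting, and they give no event rate from which to estimate how many participants would be affected. The laboratory Hy's Law summary is unaffected. This is an inexpensive consistency correction and does not threaten the trial's main safety results.

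**What to change.** 1. Reconcile Protocol 8.3.6 with SAP 8.3.1 so that one ALP condition and one set of inequality signs apply. This takes one phrase in a protocol amendment or a clarification to sites.
2. In SAP 3.9, correct the protocol reference from 8.3.1 to 8.3.6 and state the ALP difference explicitly.
3. In SAP 8.2.2, keep the AESI table based on the CRF. Replacing it with a laboratory derivation would lose the protocol's judgement about alternative explanations. Add a listing that cross-checks the CRF AESI flag against the SAP 8.3.1 laboratory Hy's Law criterion and shows the disagreements.

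The cost is a few sentences and one extra listing from data already collected.

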8.3.7 Adverse events of special monitoring

An AE of special monitoring (AESM) is a product-specific AE, adverse reaction, or safety topic requiring special monitoring by UCB.

For rozanolixizumab, the following events require immediate reporting (within 24 hours regardless of seriousness) to UCB:

- Severe and/or serious headache
- Suspected aseptic meningitis

Procedures for the management of AESM are provided in Appendix 14 (Section 10.14).

Although infections and infusion-related reactions as well as hypersensitivity reactions or anaphylaxis are not classified as AESM, these AEs will be monitored by the Investigator. If such an event is suspected it should be managed according to the guidance provided in Appendix 13 (Section 10.13). In case of suspected anaphylaxis, the Sampson's Criteria (Sampson et al, 2006) in Appendix 15 (Section 10.15) should be completed.

All AESM will follow the SAE recording and reporting procedures as indicated in Appendix 3 (Section 10.3).

8.3.8 Treatment-emergent adverse events

Treatment-emergent AEs are defined as AEs starting after the time of first IMP administration up to and including 8 weeks after the final dose.

8.4 Safety signal detection

Selected data from this study will be reviewed periodically to detect as early as possible any safety concern(s) related to the study medication so that investigators, clinical study participants, regulatory authorities, and IRBs/IECs will be informed appropriately and as early as possible.

In addition, an IDMC will periodically review and monitor safety data from this study and advise UCB. Details are provided in the IDMC Charter.

The Study Physician or medically qualified designee/equivalent will conduct an ongoing review of SAEs and perform ongoing SAE reconciliations in collaboration with the Patient Safety representative.

As appropriate for the stage of development and accumulated experience with the study medication, medically qualified personnel at UCB may identify additional safety measures (eg, AEs, vital signs, laboratory or ECG results) for which data will be periodically reviewed during the course of the study.

8.5 Treatment of overdose

For this study, any dose of increase of 10% greater than the assigned dose for each administered dose of IMP will be considered an overdose, irrespective of the weight tier band. Overdose events are only considered AEs or SAEs if there are associated clinical signs and symptoms or if the act of taking the excess IMP itself is an AE or SAE (eg, suicide attempt).

UCB does not recommend specific treatment for an overdose.

In the event of an overdose, the Investigator or treating Physician should:

1. Contact the Medical Monitor immediately.
2. Closely monitor the participant for any AE/SAE and laboratory abnormalities for at least 5 days.
3. Obtain a plasma sample for PK analysis within 3 days from the date of the last dose of study treatment if requested by the Medical Monitor (determined on a case-by-case basis).
4. Document the quantity of the excess dose as well as the duration of the overdose in the eCRF.

Decisions regarding dose interruptions or modifications will be made by the Investigator in consultation with the Medical Monitor based on the clinical evaluation of the participant.

8.6 Pharmacokinetics and antidrug antibodies

Whole blood samples will be collected for measurement of plasma concentrations of rozanolixizumab and ADA as specified in the Schedule of Activities (Section 1.3). Blood samples may be collected at additional time points during the study if warranted and agreed upon between the Investigator and the Sponsor. Instructions for the collection and handling of biological samples will be provided in the laboratory manual for this study. The actual date and time (24-hour clock time) of each sample will be recorded.

Samples will be used to evaluate the PK of rozanolixizumab and ADA and may be used for establishing assay parameters (eg, ADA cut point setting and PK selectivity assessment).

Samples collected for analyses of rozanolixizumab concentration and ADA may also be used to evaluate safety or efficacy aspects related to concerns arising during or after the study.

Participant confidentiality will be maintained. At visits during which only plasma samples for the determination of concentration of rozanolixizumab will be taken, 1 sample of sufficient volume can be used.

Any changes in the timing or addition of time points for any planned study assessments must be documented and approved by the relevant study team member and then archived in the UCB and site study files but will not constitute a protocol amendment. The IRB/IEC will be informed of any safety issues that require alteration of the safety monitoring scheme or amendment of the ICF.

8.7 Genetics

Genetics are not evaluated in this study.

8.8 Pharmacodynamics

Venous blood samples will be collected at time points specified in the Schedule of Activities (Section 1.3) for measurement of:

- Serum IgG and IgG sub-classes concentrations
- Serum MG-specific autoantibodies (anti-MuSK/anti-AChR) levels

For all PD assessments, blood samples will be collected predose. Instructions pertaining to sample collection, processing, storage, labeling, and shipping are provided in the laboratory manual for this study.

8.9 Biomarkers

Collection of samples for exploratory safety biomarker research is part of this study. Baseline values from MG0003 will serve as the Baseline value for MG0007. Safety samples must be collected 4 hours after the onset of the event, or otherwise as soon as possible within 72 hours after the onset of the event in case of AESM of severe and/or serious headache or suspected aseptic meningitis.

If not used immediately, these samples will be stored at -80°C for up to 20 years for later exploratory analyses. Any exploratory biomarker will only ever be related to the exploration of cause, progression, and appropriate treatment of MG. They may also be used to develop tests/assays including diagnostic tests related to rozanolixizumab and/or FcRn inhibitor and MG.

The nature and format of these tentative additional analyses will be determined at a later time. Details on the collection, storage, preparation, and shipping of samples will be presented in the laboratory manual provided separately. Instructions pertaining to sample collection, processing, storage, labeling, and shipping are provided in the laboratory manual for this study. Detailed information on sample analyses will be provided in a bioanalytical report.

8.9.1 Immunological assessments

Blood samples for immunological testing are required and will be collected from all study participants in this study as specified in the Schedule of Activities (Section 1.3) for the

measurement of [REDACTED] and [REDACTED]. All samples should be collected predose.

For [REDACTED] and [REDACTED] Baseline values from MG0003 will serve as the Baseline value for MG0007. Additional samples should be collected 2 hours and 4 hours postevent for study participants who experience infusion reaction or hypersensitivity reaction at the site. In case the event happens at home, additional samples should be collected as soon as possible, but prior to the next dosing as specified in the Schedule of Activities (Section 1.3).

Instructions pertaining to sample collection, processing, storage, labeling, and shipping are provided in the laboratory manual for this study.

8.10 Medical resource utilization and health economics

Medical resource utilization and health economics will be measured for this study.

9 STATISTICAL CONSIDERATIONS

A description of statistical methods follows and will be described in more detail in the Statistical Analysis Plan (SAP).

9.1 Definition of analysis sets

The definition of analyses sets are as follows:

- The Enrolled Set: All study participants who have signed the ICF.
- Full Analysis Set (FAS): All enrolled study participants who were randomized in this study or in MG0004. Study participants enrolling from MG0004 will utilize their last assigned dose level from MG0004 as their planned dose in MG0007.
- Safety Set (SS): All study participants in the FAS who received at least one dose of IMP.

